3.3.4 Adverse Event Follow-up

Any self-reported AE that remains unresolved by the end of the study should be followed up until resolution by the investigator/designee, and the resolution should be documented only as source documentation. If a subject is unreachable to determine whether the AE has been resolved, the attempts to contact the subject should be documented as source documentation. Examiner observed AEs that are unresolved at the end of the study are followed to resolution at the discretion of the Medical Monitor.

4. LABORATORY METHODS

4.1 Specimen Preparation

Extracted human teeth will be used as the hard tissue test substrate for the preparation of the ~~4 x 4 mm~~ and the 4 mm round specimens. The teeth will be collected and transported to OHRI in a saturated thymol solution. Upon receipt, the teeth will be sorted and cleaned. The teeth will then be stored in saturated thymol solution during sample preparation procedures.

[figure not shown]
Teeth will be selected based on the following criteria:

- Free of caries and major restorations;
- No discoloration and no markings, such as cracks, when viewed under a microscope at 20 \times magnification;
- Sufficient tooth surface to provide a large size specimen to meet study requirements.

A core of enamel 4 mm in diameter will be prepared from each human tooth by cutting perpendicularly to the buccal surface with a hollow-core diamond drill bit. Each block will be ground and polished to create flat surfaces [Zero et al., 1990].

The round specimens will be ground and polished to create planar parallel dentin and enamel surfaces. All grinding/polishing will be done on a polishing surface moistened with deionized water (dw). The dentin side will be ground flat using 500 grit silicon carbide paper, followed by grinding and polishing of the enamel side. A small orientation cut will be placed on each block (see Figure 2). The enamel surface of each specimen will be ground using 1200 grit silicon carbide paper followed by 2400 and then 4000 grit silicon carbide paper. After the grinding procedures are completed, the enamel specimens will be placed under running dw for three minutes, sonicated in deionized water (dw) for three minutes and then placed under running dw for three minutes. The polishing step will involve the use of a 1 micrometer (μ m) diamond suspension on a polishing cloth. The enamel specimens will then be rinsed under a steady stream of dw for three minutes, sonicated for three minutes in 2% microliquid soap and then rinsed again with dw for three minutes. Resulting specimens will have a thickness range of 1.8 to 2.2 mm. The specimen will have a minimum polished surface of 3 mm \times 3 mm in the center of the enamel surface.

Figure 2
4 mm Round Human Enamel Specimen

4.2 Lesion Creation

The round enamel specimens will be partially demineralized using a modification of the method described by White [1987]. The human enamel specimens will be immersed for 24 hours at 37° C under static conditions in 40 ml of an acid buffer (0.05 mol/L lactate), 50% saturated with respect to hydroxyapatite and with 0.2% (wt/vol) carbopol 907 (BF Goodrich Co., USA) added (pH adjusted to 5.0 using KOH or NaOH), and then rinsed thoroughly with deionized water. The demineralized enamel specimens will then be stored in a moist environment to prevent dehydration.

4.3 6.3 Lesion Quality

Lesions will be inclined towards an overhead light until a reflection is obtained. Acceptable lesions with an intact surface-zone will have a continuous, uniform shiny surface, with no matt areas. Lesions with matt area(s) will be rejected. The following criteria will be used to select specimens for inclusion in the study:

- The lesioned areas of each specimen should be of equal and uniform opacity; and
- The lesioned areas of each specimen should possess a surface shine when exposed to light, thereby indicating an intact surface.

4.4 Efficacy Measurements and Evaluations

4.4.1 Surface Microhardness

The SMH test will be used to assess changes in the mineral status of partially demineralized enamel specimens. SMH will be measured using a Wilson 2100 Hardness Tester. Each enamel specimen will be secured on a 1-inch square acrylic block with sticky wax and then placed on the microhardness tester. Five baseline indentations spaced 100 µm apart will be placed with a Knoop diamond under a 50 gram load in the center of a flattened, polished sound enamel specimen. SMH will be determined by measuring the length of the indentations using Wilson 2100 - Clemex CMT Software (version 6.0.011). For enamel specimens to be acceptable for use in the study, the mean of the five baseline indentation length must be 43 µm with a standard deviation of $\leq 3\mu\text{m}$.

After in vitro demineralization, the enamel specimens will be again SMH tested by placing five indentations 100 µm to the left of the baseline indentations (see Figure 2). To qualify for the study, the mean ($n = 5$) indentation lengths of the partially demineralized specimens must fall within a range of 100-140 µm with a standard deviation of $\leq 10 \mu\text{m}$. After 7, 14 and 21 days of intra-oral exposure the enamel specimens will be again SMH-tested by placing five indentations 100 µm to the right of the baseline indentations (see Figure 2). The extent of remineralization will be calculated based on the method of [Gelhard et al., 1979].

$$\% \text{SMH recovery} = (D1-R)/(D1-B) \times 100$$

B = indentation length (μm) of sound enamel specimen at baseline

D1 = indentation length (μm) after in vitro demineralization

R = indentation length (μm) after intra-oral exposure.

Additionally, the absolute remineralization change will be computed as: SMH change= D1-R

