2.1.1 Primary Endpoints

The primary endpoint is the enamel fluoride uptake on Day 21 and the primary comparison between pastes with 0 and 2800ppm fluoride concentrations, and all other treatment comparisons and time points being of secondary interest. The secondary endpoints include % SMH recovery and SMH change (see 4.4).

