Each subject will receive an OST examination, answer continuation questions and have their medical history/medication information updated. Subjects will be asked to return the washout product they received at Visit 2 and will be given their randomized study product and diary for product use. Subjects will be instructed on the brushing method (see Appendix). The four enamel partially demineralized specimens will be placed in the buccal flange/posterior teeth areas on one side of the subject's mandibular partial denture. All subjects will be instructed to wear their partial denture containing the enamel specimens 24 hours a day except during the cleaning of their natural teeth (twice per day) and for short periods to rinse their mouth out with tap water after meals and snacks.

Visit 4 (7 Day Removal)

Seven (7) days following Visit 3, the subjects will return to the Institute and answer continuance criteria questions and update their medical history/medication information. One enamel specimen will be removed from anterior denture tooth site of their partial denture and the hollow will be filled with a temporary dental material (DentuSil™). The subjects will be told to continue using their assigned product as instructed.

Visit 5 (14 Day Removal)

Fourteen (14) days following Visit 3, the subjects will return to the Institute and answer continuance criteria questions and update their medical history/medication information. One enamel specimen will be removed from posterior denture tooth site of their partial denture and the hollow will be filled with a temporary dental material (DentuSil™). The subjects will be told to continue using their assigned product as instructed.

Visit 6 (End Treatment Period 1)

Twenty-one (21) days following Visit 3, the subjects will return to the Institute and receive an OST examination, answer continuance criteria questions and update their medical history/medication information. Subjects will be asked to return the study product and diary they received at Visit 3. The remaining two enamel specimens in the buccal flange site will be removed from their partial denture and the hollows will be filled with a temporary dental material (DentuSil)

Period 2, 3, 4 & 5

The procedures outlined above (Visit 2-6) will be repeated until each subject has used each of the four test products, followed by a 5th test product in Period 5. At Visit 21 (and also at Visit 26 for those subjects

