5. STATISTICAL PLAN

5.1 Statistical Methods

Efficacy Analyses

The mean % SMH recovery and SMH change will be calculated using the five sets of indentations within each enamel specimen. The mean fluoride uptake will be calculated using the four samples within each enamel specimen. The mean % SMH recovery, SMH change and mean fluoride uptake will be computed for each enamel specimen at the different time points (1 specimen for 7 and 14 days and 2 specimens for 21 days) within a subject; if a subject is missing an enamel specimen for the 21-day reading, the single available enamel specimen will be used. The treatments will be compared using analysis of variance models (ANOVA) or analysis of covariance (ANCOVA) suitable for a crossover study.

To assess for potential carryover effects on the primary endpoint, the models will include random effects for subject and fixed effects for study period, product and carryover term. If the carryover term is not significant at the 0.1 level ($p>0.1$) then the final crossover model will not include the carryover term.

A repeated measures crossover model will also be carried out to explore the treatment time effect. This model will include a random effect for subject and fixed effects for study period, product, treatment times (7, 14 and 21 days) and treatment time by product interaction. For SMH change, B (indentation length (μm) of sound enamel specimen at baseline) or D1 (indentation length (μm) after challenge) will be added as a covariate in the model. Additionally, the product by covariate interaction will also be assessed in this model. A 10% significance level will be used for all product comparison tests. No alpha-level adjustments for multiple comparisons adjustments will be applied.

If the data does not satisfy the normality criterion, log transformation or analogous nonparametric methods will be employed. Additional statistical techniques may also be applied in order to more fully understand the data.

The SnF_2 product used in Period 5 will be compared to the negative control treatment used in other periods using a paired t-test.

Safety Analyses

Adverse events reported during the study will be listed in the final report.

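### The primary fluoride-uptake model names no term for starting lesion softness (D1, 100 to 140 µm, on new specimens each period); if D1 is related to uptake, the 0 v 2800 ppm estimate carries noise that could be removed

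*Combined protocol and SAP*

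**What the plan says.** All references are to the combined protocol and SAP.

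- **Endpoint (2.1.1).** "The primary endpoint is the enamel fluoride uptake on Day 21", with 0 v 2800 ppm as the primary comparison.
- **Specimens (4.1, 4.4.1).** Each specimen is a core cut from a human tooth. For sound enamel (B), "the mean of the five baseline indentation length must be 43" µm. After laboratory demineralization (D1), mean "indentation lengths of the partially demineralized specimens must fall within a range of 100-140" µm. The within-specimen SD limits are 3 µm for B and 10 µm for D1. Section 4.3 adds visual checks of opacity and shine.
- **Placement (2.1.5, Visit 3, repeated in each period).** "The four enamel partially demineralized specimens will be placed in the buccal flange/posterior teeth areas". Section 3.1.2 randomizes subjects to treatment sequences. No section says how qualifying specimens are allotted to subjects or periods.
- **Readings (5.1).** "1 specimen for 7 and 14 days and 2 specimens for 21 days".
- **Analysis (5.1).** In general, "The treatments will be compared using analysis of variance models (ANOVA) or analysis of covariance (ANCOVA) suitable for a crossover study". For the primary endpoint, "the models will include random effects for subject and fixed effects for study period, product and carryover term". For SMH change, B or D1 (the length "after challenge) will be added as a covariate in the model").

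**The concern.** A crossover removes differences between mouths because each subject is his or her own control. It does not remove differences between specimens, because each product is tested on a different set. D1 is known for every specimen before placement and cannot be affected by the product, so it is a legitimate covariate. The plan already treats starting hardness as worth adjusting for in one secondary endpoint, yet names no such term for the primary one. EFU is drilled from the same lesions, so a dependence on their starting state is plausible.

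At stake is the precision of the product contrasts in EFU. Section 5.3 says the 16 subjects were chosen for logistical reasons, and 5.4.1 sets a floor of 10 completers. No power calculation therefore shows that there is precision to spare.

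**Working it through.** The plan gives no power, effect size, EFU variance or D1-EFU correlation, so there is no figure of its own to reproduce.

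**1. Spread the criteria allow.** With B = 43 µm, softening D1 - B runs from 100 - 43 = 57 µm to 140 - 43 = 97 µm, a ratio of 97/57 = 1.7.

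**2. Spread between products (distribution assumed).** If D1 is uniform over the window, its SD is 40/√12 = 11.5 µm per specimen. For a Day 21 pair mean it is 11.5/√2 = 8.2 µm, and for the difference between two products within a subject 8.2 × √2 = 11.5 µm. If D1 is bell-shaped (window equal to 6 or 4 SD), the per-specimen SD is 40/6 = 6.7 to 40/4 = 10 µm. Averaged over 16 subjects, the chance SE of the D1 difference between two products is 11.5/√16 = 2.9 µm (uniform), or 1.7 to 2.5 µm (bell-shaped).

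**3. Effect of adding D1 to the EFU model.** Let r be the within-subject correlation of the pair-mean D1 with EFU (assumed). With complete data and no carryover term, residual df = 64 observations - 16 subjects - 3 periods - 3 products = 42, or 41 with D1. Specimens are taken to reach periods independently of product. The variance of a product contrast is then multiplied by about

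(1 - r²) × [1 + 1/(df - 2)] = (1 - r²) × (1 + 1/40) = 1.025 × (1 - r²).

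| Assumed r | Formula, n=16 | Simulated crossover, n=16 | Change in variance |
|---|---|---|---|
| 0 | 1.025 | 1.03 | about +3% |
| 0.2 | 1.025 × 0.96 = 0.98 | 0.98 | about -2% |
| 0.3 | 1.025 × 0.91 = 0.93 | 0.94 | about -6 to -7% |
| 0.5 | 1.025 × 0.75 = 0.77 | 0.78 | about -23% |

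Break-even is where 1.025 × (1 - r²) = 1, so r² = 1/41 and r is about 0.16.

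With 10 complete subjects, df = 40 - 10 - 3 - 3 = 24 and the multiplier is (1 + 1/22) × (1 - r²): 1.05, 1.00, 0.95 and 0.78 at the same correlations.

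**4. Effect on the test.** Simulated at a two-sided 10% level (two-sided assumed, because the hypotheses are non-directional) with n = 16:

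- True difference of 1 within-subject SD: power is about 0.87 without D1. With D1 it is about 0.86, 0.88, 0.89 and 0.94 at r = 0, 0.2, 0.3 and 0.5.
- True difference of 2 within-subject SD: power is about 1.00 either way.
- No true difference: the rejection rate stays near 0.10 with or without D1.

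**The case against.** The strongest reply is that no evidence in the documents links D1 to EFU. Section 1.1 gives a 30:1 ratio of indentation length to depth, so D1 of 100 to 140 µm reflects about 3.3 to 4.7 µm of penetration. EFU is drilled to about 100 µm and expressed per core area (4.4.2). Surface hardness may say little about uptake at that depth. This stands: the gain is conditional, and at r of about 0.2 or less it is close to nothing.

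Other points that stand:

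- SMH change already has a B or D1 covariate, and % SMH recovery is already scaled by D1 - B. The point is confined to EFU.
- The general wording in 5.1 leaves room for a covariate. The fair description is that D1 is not specified for EFU, not that it is excluded.
- Averaging two specimens at Day 21 already halves the variance between specimens.

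Two points carry less weight. The SD limits in 4.4.1 control spread within a specimen, not between specimens. The visual checks in 4.3 set no limit on D1 beyond the 100 to 140 µm window.

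A reader might infer more than the documents support. One such inference is that lesion differences bias the product comparisons, or the Period 5 paired comparison, in which all subjects receive one product in a separate period. The plan is silent on allocation. Silence neither shows that specimens were steered by product or period nor shows that they were allotted independently. Another is that a product may well be tested on pairs near 100 µm and its comparator on pairs near 140 µm. That 40 µm gap is about 40/11.5 = 3.5 SD of the within-subject difference, so it would be rare under independent allocation.

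**Conclusion.** The concern holds as a conditional point about precision in the primary EFU analysis. The admission window is wide, new specimens are used in each period, and 5.1 names no D1 term for EFU. Whether this costs anything depends on a correlation that the documents do not give. Over assumed values from 0 to 0.5, the covariate moves the variance of the 0 v 2800 ppm estimate from about 3% worse to about 23% better at n = 16. The figures assume complete data, no carryover term and allocation of specimens independent of product.

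No bias and no inflation of type I error is shown. If the true 0 v 2800 ppm difference is 2 within-subject SD or more, the primary test is unaffected in practice, and EFU contrasts between closer fluoride levels stand to gain most. The case for acting is the asymmetry: a small known cost against a possible material gain. The choice should be made now, because adding a covariate after seeing the results would be data-driven.

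**What to change.** **Recommended, in 5.1.** State, before unblinding, that the primary Day 21 EFU model includes as a covariate the mean D1 of the specimens contributing to the reading (the single specimen's D1 where only one is available). The cost is one sentence and one degree of freedom (42 to 41 with complete data). The variance rises by about 3% at n = 16 if D1 is unrelated to EFU, and by about 5% at n = 10. D1 is already measured on every specimen, so no new data are needed.

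**Optional, in section 4 and Visit 3.** Assign qualifying specimens to subject-periods from a computer list made without knowledge of product, balanced on D1 as far as stock allows. This would put on record that specimens reach periods independently of product. No fixed matching tolerance is proposed: the documents give no basis for one, and tight matching could require up to 16 × 4 × 2 = 128 flange specimens prepared ahead. The gains shown in the working are for the covariate, not for matching.

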4.4.2 Enamel Fluoride Uptake

The microdrill enamel biopsy technique as described by [Sakkab et al., 1984] will be used to analyze the fluoride content of the partially demineralized enamel specimens. Each enamel specimen will be mounted perpendicular to the long axis of a drill bit attached to a specially designed microdrill, and drilled to a depth of $\sim 100 \mu\text{m}$ through the entire lesion (four cores per specimen; see Figure 2).

The drilling and sample collection will be performed in a static-controlled atmosphere to prevent loss of enamel powder due to charging effects. The enamel powder sample, pooled from the four drilling samples, will be transferred to an analyzer cup cap. 20 microliters (μl) of 0.5 Molar (M) Perchloric Acid (HClO_4) will be added to the enamel powder and the cap gently swirled to dissolve the powder. To the analyzer cap containing the 20 μl of HClO_4 /enamel powder, 40 μl of citrate/ethylene-diamine-tetraacetic acid (EDTA) buffer and 40 μl of de-ionized water will be added and immediately analyzed for fluoride

content using a fluoride specific electrode and pH/Ion meter. The diameter of the drill hole will be determined using a calibrated microscope interfaced with an image analysis system. The amount of fluoride-uptake by enamel will be calculated based on the amount of fluoride divided by the area of the enamel cores and expressed as $\mu\text{g F}/\text{cm}^2$.

4.5 Laboratory Data

As each specimen is analyzed, individual Excel files will be generated and imported into a validated relational database management system. After the analyses are completed, all enamel specimen surface microhardness, and enamel fluoride uptake data will be reviewed by the principal investigator before secure transfer to the sponsor. The investigator will document this review and documentation will be filed with the laboratory study files.

4.6 Specimen Retention

Laboratory specimens will be retained by the study site for twelve months following database lock.

5. STATISTICAL PLAN

5.1 Statistical Methods

Efficacy Analyses

The mean % SMH recovery and SMH change will be calculated using the five sets of indentations within each enamel specimen. The mean fluoride uptake will be calculated using the four samples within each enamel specimen. The mean % SMH recovery, SMH change and mean fluoride uptake will be computed for each enamel specimen at the different time points (1 specimen for 7 and 14 days and 2 specimens for 21 days) within a subject; if a subject is missing an enamel specimen for the 21-day reading, the single available enamel specimen will be used. The treatments will be compared using analysis of variance models (ANOVA) or analysis of covariance (ANCOVA) suitable for a crossover study.

To assess for potential carryover effects on the primary endpoint, the models will include random effects for subject and fixed effects for study period, product and carryover term. If the carryover term is not significant at the 0.1 level ($p>0.1$) then the final crossover model will not include the carryover term.

A repeated measures crossover model will also be carried out to explore the treatment time effect. This model will include a random effect for subject and fixed effects for study period, product, treatment times (7, 14 and 21 days) and treatment time by product interaction. For SMH change, B (indentation length (μm) of sound enamel specimen at baseline) or D1 (indentation length (μm) after challenge) will be added as a covariate in the model. Additionally, the product by covariate interaction will also be assessed in this model. A 10% significance level will be used for all product comparison tests. No alpha-level adjustments for multiple comparisons adjustments will be applied.

If the data does not satisfy the normality criterion, log transformation or analogous nonparametric methods will be employed. Additional statistical techniques may also be applied in order to more fully understand the data.

The SnF_2 product used in Period 5 will be compared to the negative control treatment used in other periods using a paired t-test.

Safety Analyses

Adverse events reported during the study will be listed in the final report.

5.2 Hypotheses

The following hypothesis will be tested for each index and each time point:

Null: there is no difference between the treatments using pastes with different fluoride level.

Alternative: there is a difference between at least two treatments with different fluoride level.

Period 5 Hypotheses:

Null: there is no difference between SnF₂ and the negative control.

Alternative: there is a difference between SnF₂ and the negative control.

5.3 Number of Subjects

The number of subjects (16) was chosen for logistical reasons for this study.

